5.5 IMPUTATION FOR PARTIAL OR MISSING DATES

Partial or missing admission and discharge dates for hospitalizations will not be imputed.

If dates are missing or incomplete for an AE (including deaths) or concomitant medication, the following algorithm will be used for imputation:

Table 2. Imputation Rules for Partial or Missing Start Dates

	Stop Date			
Start Date	Complete: yyyymmdd	Partial: yyyymm	Partial: yyyy	missing

		<1 st dose	≥1 st dose	<1 st dose yyyyymm	≥1 st dose yyyyymm	<1 st dose yyyy	≥1 st dose yyyy	
Partial: yyyyymm	= 1 st dose yyyyymm	2	1	n/a	1	n/a	1	1
	≠ 1 st dose yyyyymm		2	2	2	2	2	2
Partial: yyyy	= 1 st dose yyyy	3	1	3	1	n/a	1	1
	≠ 1 st dose yyyy		3		3	3	3	3
Missing		4	1	4	1	4	1	1

- 1 = Impute the date of first dose
- 2 = Impute the first of the month
- 3 = Impute January 1 of the year
- 4 = Impute January 1 of the stop year

Note: If the start date imputation leads to a start date that is after the stop date, then do not impute the start date.

Imputation rules for partial or missing stop dates:

1. Initial imputation
 - a. For partial stop date “mmyyyy”, impute the last of the month.
 - b. For partial stop date “yyyy”, impute December 31 of the year.
 - c. For completely missing stop date, do not impute.
2. If the stop date imputation leads to a stop date that is after the death date, then impute the stop date as the death date.
3. If the stop date imputation leads to a stop date that is before the start date, then there is a data error and do not impute the stop date (i.e. set the stop date as missing).

Imputation rules for partial or missing death dates:

1. If death year and month are available but day is missing:

- a. If “mmyyyy” for last contact date = “mmyyyy” for death date, set death date to the day after the last contact date.
 - b. If “mmyyyy” for last contact date < “mmyyyy” for death date, set death date to the first day of the death month.
 - c. If “mmyyyy” for last contact date > “mmyyyy” for death date, data error and do not impute.
2. If both month and day are missing for death date or a death date is totally missing, set death date to the day after the last contact date.

The imputed dates will be used to assess whether AEs should be considered as treatment-emergent and if concomitant medications should be included in the safety summaries, however the original, partial dates will be included in data listings.

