5.4 SAFETY

Event of Interest (EOI)

An EOI is defined as a noteworthy event for a particular product or class of products that a sponsor may wish to monitor carefully. It could be serious or non-serious, and could include events that might be potential precursors or prodromes for more serious medical conditions in susceptible individuals (Council for International Organizations of Medical Sciences (CIOMS) VI, 2005). The EOIs that will be monitored in this study are:

- infusion reactions
- tumor lysis syndrome
- cardiac disorders
- serious infections
- severe mucocutaneous reactions
- hematological toxicity
- progressive multifocal leukoencephalopathy
- GI perforation

AE preferred terms that are potentially representative of the EOI will be retrieved for review and analysis using the latest version of pre-specified Standardized MedDRA Queries (SMQs) if available.

Infusion reaction and tumor lysis syndrome EOIs will be summarized separately for:

- all events and
- events with onset day coincident with first IP infusion or the day after the first IP infusion.

If no SMQ is available for use as a search tool for a given EOI (e.g, infusion reactions) a customized search strategy will be developed and the preferred terms used in that search will be provided in an appendix to the SAP prior to the database lock.

Exposure-adjusted Incidence Rates of Adverse Events

Exposure-adjusted incidence rate is calculated as the number of subjects in a treatment group that experienced the event at least once divided by the total subject exposure times in the group. For subjects who experience the event, the exposure time is calculated as the time from the first dose date of IP to the onset of the first event. For subjects who do not experience the event, the exposure time is calculated as the time from the first dose of IP to the minimum of the end of study (EOS) visit date and death date.

Last Known Date Alive

The last known date alive will be the maximum of: end of study date, non-fatal AE start and stop dates, IP administration dates, serum chemistry and hematology sample collection dates, ADA sample collection dates, concomitant medication dates, vital sign dates, PK sample collection dates, and NHL lesion assessment dates.

Overall Survival (OS)

On-study OS is defined as the time from randomization to the date of death. Subjects who have not died before the week 28/EOS visit will be censored for OS at the last known date alive on or prior to EOS.

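### SAP 5.5 treats a death date with a known year as if nothing were known, so the imputed date can contradict the recorded year of death

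*SAP*

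**What the plan says.** SAP section 5.5 has two rules for incomplete death dates.

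- **Rule 1, year and month known.** If the month matches that of last contact, the death is placed the day after last contact (1a). If the death month is later, the plan says "set death date to the first day of the death month" (1b). If it is earlier, the instruction is "data error and do not impute" (1c).
- **Rule 2, everything else.** The trigger is "If both month and day are missing for death date or a death date is totally missing". The action is the same for both cases: "death date is totally missing, set death date to the day after the last contact date".

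On scope, the section opens with "If dates are missing or incomplete for an AE (including deaths) or concomitant medication, the following algorithm will be used for imputation". On use, it closes with "The imputed dates will be used to assess whether AEs should be considered as treatment-emergent and if concomitant medications should be included".

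SAP section 5.4 states "On-study OS is defined as the time from randomization to the date of death" and counts death from any cause as a PFS event. Neither definition refers to section 5.5 or gives its own rule for a partial death date. The term used in section 5.5, last contact date, is not defined. Section 5.4 defines a different term: "The last known date alive will be the maximum of: end of study date", followed by a list of other dates.

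**The concern.** A year-only death date carries information, and rule 2 discards it. If last contact was in one year and the death is recorded in the next, rule 2 returns a date in the wrong year. If the recorded year precedes last contact, the record is internally inconsistent. Rule 1c would stop and flag that, whereas rule 2 imputes a date.

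The stake is the date of death wherever it is used. Within section 5.5 it caps imputed stop dates. In section 5.4 it can end exposure time for the exposure-adjusted adverse event rates. If imputed dates are also used for OS and PFS, it fixes the event time and decides whether the death falls on study at all.

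**Working it through.** **Rules compared.** All year-only and year-month rules below are from SAP section 5.5.

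| Known part | Relation to last contact or first dose | Imputed date | Known part kept? |
|---|---|---|---|
| Death, year and month | later month | first of that month | yes |
| Death, year and month | earlier month | none, data error | yes |
| Death, year only | later year | day after last contact | **no** |
| Death, year only | earlier year | day after last contact | **no** |
| Start date, year only | same or different year from first dose | first dose date or 1 January of that year | yes |
| Stop date, year only (initial step) | any | 31 December of that year | yes |

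**Size of the date error.** The plan gives no figure to reproduce, so all calendar dates here are assumptions. For a death year one later than the last-contact year:

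minimum error = (1 January of death year) − (last contact + 1 day)

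With death recorded only as 2018:

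| Last contact | Imputed death | Days before 1 January 2018 |
|---|---|---|
| 1 Sep 2017 | 2 Sep 2017 | 121 |
| 15 Oct 2017 | 16 Oct 2017 | 77 |
| 20 Nov 2017 | 21 Nov 2017 | 41 |
| 20 Dec 2017 | 21 Dec 2017 | 11 |

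From week 4 the dosing and end-of-study visits are 8 weeks apart with windows of ±7 days (Protocol Table 1 and section 9.6). On those windows alone, consecutive contacts are at most 56 + 14 = 70 days apart. The 121- and 77-day examples therefore need missed visits or loss to follow-up; the 41- and 11-day examples do not.

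**Effect on OS, if rule 2 is used for it.** Time = event date − randomization date + 1 (SAP section 5.2), and week 28 is randomization + 196 days.

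- *Shifted event.* Randomized 1 Aug 2016, last contact 22 Aug 2016, death recorded as 2017. Rule 2 gives 23 Aug 2016, day 23. The earliest date the record allows is 1 Jan 2017, day 154, which is still before week 28 (13 Feb 2017). The event is at least 154 − 23 = 131 days early.
- *Event created.* Randomized 4 Apr 2016, last contact 25 Apr 2016, death recorded as 2017. Rule 2 gives 26 Apr 2016, an on-study death at day 23. The earliest possible death is day 273, after week 28 (17 Oct 2016), so the record calls for censoring.

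**Effect on the hazard ratio.** A Cox estimate uses event times only through the numbers at risk. As a check, 125 subjects per arm were simulated with about 10% early dropout, deaths split equally between arms and no stratification (all assumed), and one late death was moved 121 days earlier. The hazard ratio changed by at most about 6% with 2 deaths in total, 3% with 4, and 2 to 3% with 6 to 10. Adding a false event matters more. With equal numbers at risk, going from d to d + 1 deaths in one arm multiplies the ratio by about (d + 1)/d: 2.0 for d = 1, 1.5 for d = 2 and 1.2 for d = 5. The documents give no expected number of deaths, so d is an assumption.

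**The case against.** The strongest objection concerns use. The closing sentence of section 5.5 names only treatment-emergent status and concomitant medications. A reader might infer that the SAP puts imputed death dates into OS and PFS, but it does not say so. That part of the objection stands. What remains is that OS and PFS need a death date and no other rule exists. Either rule 2 applies and can return an impossible date, or the plan has no rule for these endpoints.

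A reader might also infer that a single misdated death would visibly change the survival results. For a change of date alone this is not supported: the hazard ratio moves by a few percent, far less than its uncertainty with so few events. Only a falsely created event would have a noticeable effect.

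Nor can one conclude that the rule both pulls later deaths into the study and drops on-study deaths. These need opposite readings of last contact date. The first needs last contact before the end-of-study date. The second needs last contact to be the end-of-study date, so that the day after falls outside the window. The SAP chooses neither reading, so only the missing definition can be criticized.

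Finally, the trigger is unlikely. A fatal event is a serious adverse event reportable within 24 hours of the investigator's knowledge (Protocol 11.2), and SAP section 8.2 provides for data screening and a review meeting before lock. A year-only date would probably be queried. It could still survive, for example for a subject whose death is found in public records after withdrawal of consent, which Protocol 8.4.3.1 allows where permitted. Enrollment of about 24 months also means follow-up will cross year ends. This limits the importance of the point without removing it.

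**Conclusion.** Rule 2 is wrong as written for year-only death dates. It can place a death in a year the record excludes, and it lacks the conflict check of rule 1c. For a totally missing date, or when the death year equals the last-contact year, it is unobjectionable.

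Materiality is low. Among about 250 subjects followed to week 28, probably none or one will be affected. That is a judgment, not a figure from the documents. The Protocol synopsis calls the OS and PFS hazard-ratio intervals descriptive, inference is confined to the primary endpoint (SAP 9.5.3), and the analysis of overall response rate by week 28 does not use death dates imputed under this rule. The consequence for OS and PFS is conditional on the rule being applied to them. In that case the worst outcome is one on-study event that the record rules out.

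**What to change.** Make these changes in SAP2, which section 1 of the SAP already schedules before database lock:

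1. Split rule 2 for a death date with only the year known. Same year as last contact: day after last contact. Later year: 1 January of the death year, parallel to rule 1b. Earlier year: data error, do not impute, parallel to rule 1c.
2. Keep the present rule only for a totally missing death date.
3. Define last contact date and state how it relates to last known date alive, in particular whether the end-of-study date counts.
4. State whether imputed death dates are used for OS and PFS.

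The cost is a few lines of text and a small change to the derivation program. No data collection changes. Settling it before lock avoids a later decision about an individual death.

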6. ANALYSIS SETS

6.1 FULL ANALYSIS SET

The full analysis set (FAS) includes all subjects randomized in the study. Analyses for the FAS will be based on randomized treatment assignment.

6.2 PER PROTOCOL SET

The per protocol (PP) analysis set is a subset of the FAS which includes subjects who have completed all 4 weekly IP doses or who permanently ended IP prior to completing 4 weekly IP doses due to reasons allowed per protocol (ie, disease progression, adverse events and death), had at least one post-baseline tumor assessment, and did not experience a protocol deviation that would affect their evaluation for the primary objective of the study. The protocol deviations that affect evaluation for the primary objective will be determined based on a blinded data review prior to database lock.

Analyses for the PP analysis set will be based on actual treatment received.

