8.1 Overall Study Design and Plan

This is a randomized, double-blind study in adult subjects with Grade 1, 2 or 3a follicular B-cell NHL and low tumor burden. Approximately 250 subjects (125 per treatment group) will be randomized (1:1) to receive investigational product (IP) (ABP 798 or rituximab) at a dose of 375 mg/m² administered as an intravenous (IV) infusion once weekly for 4 weeks followed by dosing at weeks 12 and 20. Tumor assessment will be performed at baseline and weeks 12 and 28. Subjects will be stratified by geographic area and age (> 60 vs ≤ 60 years).

A subject will remain in the treatment phase until week 28. Subjects who discontinue IP before week 20 will be followed for 8 weeks after the last dose of IP and then complete the end-of-study (EOS) visit.

An independent data monitoring committee (DMC) will evaluate the safety data throughout the study, including an initial safety review after the first 12 subjects have received at least 2 doses of IP.

Figure 1. Study Diagram

* Response assessments at study weeks 12 and 28
Wk = week

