8.4.3.2 Evaluations at Withdrawal

For any subject who is withdrawn before completing all treatment visits, the Investigator should:

- perform all the procedures scheduled for the EOS visit (ie, week 28 visit [[Section 9.6](#)]). The week 28/EOS assessments will be performed 8 weeks (± 7 days) after the last dose of IP (unless the subject withdraws consent to do so). Computed tomography is only required at early withdrawal if it has not been performed within the previous 28 days. **Computed tomography is to be performed before the start of new anti-cancer treatment.**
- complete all appropriate electronic case report form (eCRF) screens, providing the date of and explanation for the subject's withdrawal/discontinuation.
- when indicated, arrange for appropriate follow up and/or alternative medical care of the discontinued subject.

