9.6 Week 28/End of Study

For subjects completing the treatment phase, the EOS visit will be at week 28, 8 weeks (± 7 days) after the last dose of IP. For subjects who do not complete the treatment phase, the EOS visit will be 8 weeks (± 7 days) after the last dose of IP. **Subjects who discontinue from the study due to disease progression should have a CT scan (as described below) prior to initiation of new anti-cancer treatment, if deemed clinically acceptable.**

At the EOS visit (**week 28 or 8 weeks after the last dose of IP**), the following assessments will be performed:

- physical examination, including evaluation of body systems
- vital signs (systolic and diastolic blood pressure, pulse, respiration rate, and temperature)
- standard 12-lead ECG
- ECOG performance status
- clinical disease assessment
- CT (not required if performed within the previous 4 weeks) of the neck (if palpable lymph node >1.0 cm or if performed at baseline), chest, abdomen, and pelvis.
- bone marrow biopsy (only required if bone marrow involvement is identified at baseline **for CR confirmation; if a confirmatory bone marrow assessment is not obtained, these subjects should be considered as only having a PR**). **The bone marrow biopsy can be performed at ± 14 days in relation to the study visit date.**
- clinical laboratory testing, including serum chemistry and hematology
- collection of samples for PK, antidrug antibodies, CD19+ cell count, and IgG and IgM levels

Any changes in concomitant medications since the last assessment will be recorded.

Any additional treatment for lymphoma will be recorded. All AEs, including increases in severity or frequency of pre-existing conditions, will be recorded in the eCRF through the week 28 visit. SAEs will be reported as outlined in [Section 11.2.2](#). Any SAEs ongoing at week 28 will be followed until they resolve or are considered chronic or stable.

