12.5.2 Per-protocol Set

The per-protocol analysis set is a subset of the FAS that includes subjects who have completed all 4 weekly IP doses or who permanently ended IP prior to completing 4 weekly IP doses due to reasons allowed per protocol (ie, disease progression, adverse events and death), had at least one post-baseline tumor assessment, and did not experience a protocol deviation that would affect their evaluation for the primary objective of the study. The protocol deviations that affect evaluation for the primary objective will be determined based on a blinded data review prior to database lock.

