3. STUDY DESIGN

This is a randomized, double-blind study in adult subjects with Grade 1 or 2 follicular B-cell non-Hodgkin lymphoma (NHL) and low tumor burden. Approximately 250 subjects (125 per treatment group) will be randomized (1:1) to receive investigational product (IP) (ABP 798 or rituximab) at a dose of 375 mg/m² administered as an intravenous (IV) infusion once weekly for 4 weeks followed by dosing at weeks 12 and 20. Tumor assessment will be performed at baseline and weeks 12 and 28. Subjects will be stratified by geographic region and age (> 60 vs. ≤ 60 years).

The primary efficacy endpoint is the risk difference of the overall response rate by week 28. Response to treatment will be assessed according to 1999 IWG-NHL criteria (Cheson et al,

1999). Investigators will assess the status of each subject's follicular B-cell NHL at baseline and weeks 12 and 28. Assessment will include physical examination and radiographic examination. Copies of all scheduled and unscheduled screening and on-study computed tomography (CT) scans performed to monitor or diagnose NHL must be submitted to the central imaging vendor, Perceptive Informatics, Inc. See the Independent Review Charter for details on the independent review of the imaging and clinical data.

A subject will remain on study until week 28. Subjects who discontinue IP before week 20 will be followed for 8 weeks after the last dose of IP and then complete the end of study visit.

An independent data monitoring committee (DMC) will evaluate the safety data throughout the study, including an initial safety review after the first 12 subjects have received at least 2 doses of IP. No formal interim analysis is planned.

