9.5.2 Methods for Handling Dropouts and Missing Data

Subjects without measurable disease at baseline or without post-baseline disease assessments will be counted as nonresponders in calculating the ORR.

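### The per-protocol set allows early stops for death and progression, but its scan condition removes nearly every subject who dies before a scan and any progressor never scanned

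*SAP*

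**What the plan says.** SAP 6.2 and protocol 12.5.2 define the PP set in the same words. A subject must have had all four weekly doses, or have stopped earlier "due to reasons allowed per protocol (ie, disease progression, adverse events and death), had at least one post-baseline tumor assessment". The protocol sentence continues: "had at least one post-baseline tumor assessment, and did not experience a protocol deviation that would affect their evaluation". So three conditions apply together: doses received or an allowed early stop, a post-baseline tumor assessment, and no relevant deviation.

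On the timing of assessments:

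- Protocol 8.1: "Tumor assessment will be performed at baseline and weeks 12 and 28".
- Protocol 8.4.3.2, for subjects who withdraw before completing treatment: "The week 28/EOS assessments will be performed 8 weeks (± 7 days) after the last dose of IP". The same section adds: "Computed tomography is only required at early withdrawal if it has not been performed within the previous 28 days".
- Protocol 9.6, for subjects who leave because of progression: a CT "prior to initiation of new anti-cancer treatment, if deemed clinically acceptable".

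On missing assessments, SAP 9.5.2 says that subjects "without post-baseline disease assessments will be counted as nonresponders in calculating the ORR". SAP 9.5.1.1 bases the primary analysis on the FAS, which is everyone randomized. SAP 9.5.1.2 repeats it on the PP set as one of two robustness checks. The other uses the investigator's assessment on the FAS.

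**The concern.** The definition says that stopping early because of death or progression should not cost a subject a place in the PP set. The next condition takes that place away from anyone who died before a scan could be done, and from any progressor who was never scanned. These are treatment failures, and they leave because of something that happened after randomization.

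The PP analysis is there to test whether the equivalence conclusion is robust. If such failures were more frequent in one arm, the FAS would show it in the response rate and the PP analysis would not. When the excess lies in the arm with the lower response rate, the PP difference moves toward zero, and the check looks more reassuring than it should.

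**Working it through.** The plan gives no figure to reproduce on this point. The sample-size assumptions in protocol 12.2 are redacted, so response rates below are assumptions.

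**Step 1: can a subject who dies before dose 4 have a planned scan?**

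Doses 1 to 4 fall on days 1, 8, 15 and 22 (weekly dosing, protocol 8.3). The week 12 scan falls on day 11 × 7 + 1 = 78, with a window of ± 7 days (71 to 85). The end-of-study (EOS) CT for an early stopper falls on the last-dose day + 56, ± 7 days:

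| Last dose received | Dose day | EOS CT day | Window |
|---|---|---|---|
| 1 | 1 | 57 | 50 to 64 |
| 2 | 8 | 64 | 57 to 71 |
| 3 | 15 | 71 | 64 to 78 |

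A subject whose dosing ended before about day 22 because of death reaches none of these dates. Only a chance unscheduled scan would admit that subject. The same condition removes a subject who completes four doses and then dies unscanned before week 12.

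**Step 2: what happens to progression and adverse-event stoppers?**

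They have an EOS CT due between days 50 and 78. The baseline CT precedes randomization, so by day 50 it is more than 28 days old and does not waive the EOS CT. A subject who attends as planned has a post-baseline scan and stays in the PP set. A progressor is lost only when no scan is obtained, either because it is not clinically acceptable (protocol 9.6) or because consent is withdrawn (protocol 8.4.3.2).

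**Step 3: how far does the PP response rate move?**

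Take an arm of 125 with r responders, and let the PP rule delete k unscanned failures and nobody else. The rise is r/(125 − k) − r/125.

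- r = 94: 94/125 = 75.2%. With k = 1, 94/124 = 75.8%, a rise of 0.6 points. With k = 3, 94/122 = 77.0%, a rise of 1.85 points.
- Over assumed rates of about 70% to 90% (r = 88, 100, 112), the rise is 0.57 to 0.72 points for k = 1, 1.73 to 2.20 for k = 3, and 2.93 to 3.73 for k = 5.
- k = 0 gives no change.

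**Step 4: could it change a conclusion?**

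Use an unadjusted Wald 1-sided 95% lower limit and the −15% margin, with 100/125 responders on rituximab and 92 on ABP 798.

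- Failure kept, 92/125: −6.40 − 1.645 × 5.32 = −15.16%, which misses the margin.
- Failure deleted, 92/124: −5.81 − 1.645 × 5.31 = −14.55%, which meets it.

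One subject can therefore separate the FAS and PP results, but only in a borderline trial. The planned model adjusts for region and age, so its limits would differ somewhat.

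**The case against.** A reader might infer that the rule removes early progression and adverse-event stoppers in general, because the first routine scan is at week 12. The documents do not support that. The PP condition asks for any post-baseline assessment, early stoppers have a CT due earlier (Step 2), and unscheduled scans also go to the central vendor: SAP 3 covers "Copies of all scheduled and unscheduled screening and on-study computed tomography (CT) scans performed". Nor does the clinical-acceptability wording in protocol 9.6 excuse adverse-event stoppers from a CT, since it concerns only subjects leaving because of progression.

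Tumor assessment is not defined in the PP rule. Table 1 of the protocol schedules a clinical disease assessment at every treatment visit, and protocol 10.1 includes physical examination in response assessment. If a clinical assessment counted, many early deaths would stay in. Protocol 8.1 and SAP 3 attach tumor assessment to baseline and weeks 12 and 28, which favors the imaging reading, but the ambiguity is real.

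Requiring an outcome assessment is also a defensible choice for a PP set when the FAS already imputes nonresponse. The exclusions would be visible: they are tabulated with reasons (protocol 12.6.3, SAP 9.1), and fatal events and overall survival are reported separately (SAP 9.8.2, 9.8.7). Deleting failures does not always favor equivalence. If they lie in the arm with the higher response rate, the PP difference widens.

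All of this limits the consequence. None of it explains why death is listed as an allowed reason if the next condition admits almost nobody who died.

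**Conclusion.** The point holds in a narrow form. If tumor assessment means imaging, the allowance for death before dose 4 is close to empty, and progressors for whom no scan is obtained are dropped, although the FAS counts both as nonresponders. A reader might go further and infer that the primary result is at risk. It is not, because the FAS keeps every randomized subject.

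The effect is about 0.6 points on one arm's PP response rate per deleted failure, assuming a response rate of about 75% and 125 per arm. It is zero if there are no such subjects. The number of early failures is not known. Entry requires low tumor burden and ECOG 0 or 1, so few early deaths would be expected, but the documents give no rate. This is a low-priority correction to a sensitivity analysis, worth making because it is cheap and restores what the definition says it intends.

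**What to change.** In SAP2, which SAP 1 says will be issued before database lock, reword the condition in SAP 6.2 along these lines: *at least one tumor assessment after baseline, or death or documented disease progression before one was obtained*. State that subjects admitted by the second part count as nonresponders in the PP analysis, as in the FAS. Also state whether tumor assessment means CT or includes a clinical disease assessment.

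Keep the scan condition for everyone else, including adverse-event stoppers. Their response is unknown without a scan, and imputing nonresponse for them would be a debatable choice that moves the PP set toward a copy of the FAS.

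Align protocol 12.5.2 at the next amendment, since a protocol change has to go through that process (protocol 15.2). The cost is about a sentence in each document, with no new data or visits. The downside is a slightly lower PP response rate.
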